### 3.3 Data Collection and Follow-up for Midway-Withdraw Subjects

If the investigator or the clinician or medical team providing the medical service believes that the subject needs to withdraw from the trial, it must be accepted from the medical point of view. It is the participants' freedom to determine whether continue follow-up after surgery or not. However, it is unavoidable that those midway-withdraw subjects will lead to biased outcome and the efficacy of the clinical trials will be worsen. Investigators need to collect and record the reasons and adverse events to any violation of the protocol as far as possible. The follow-up of maternal is also needed for safety issues. Maternal is still free to quit the program after completing the randomization. We will have to keep a record for the quit. Meanwhile, whether maternal agrees to be followed is also necessary to be recorded, if the participant decides to withdraw the study. If the subject explicitly requests to return all the data records, their decisions should be respected and be recorded to the final study form. When maternal is unable to obtain the informed consent during the trial, it turns to her legal representative's decision of whether continue or not.

## 4 Study Procedure

### 4.1 Flow Chart of Study

### 4.2 Informed Consent Acquisition Process

#### 4.2.1 Elective Cesarean Section

Selected maternal in cesarean section will receive detailed information. They will

also have the opportunity to ask questions after the appointment of surgery. The paper version informed consent will also be obtained on the day of admission to the ward or the day of operation. The informed consent forms need to make it clear that they can withdraw from the trial at any time for any reason, without discrimination and without any justification for their withdrawal from the trial. Randomization will be carried out on the day of operation.

#### 4.2.2 Emergency Cesarean Section

For independent randomized controlled trials of intraoperative cell salvage, it is a huge challenge to obtain informed consent during emergency cesarean section. Subjects in this group will be a special category among all participants. They will obtain particular benefits from this technology, therefore their participation is very important.

Emergency cesarean section also requires a paper informed consent form. The informed consent forms also need to make it clear that they can withdraw from the trial at any time for any reason, without discrimination and without any justification for their withdrawal from the trial. Randomization will be carried out on the day of operation.

Mostly, when there's no fetal distress during the emergency cesarean section, anticipate adequate time will be required for routine anesthesia. Therefore, after patients' decision of having a cesarean section, there is still some time to obtain informed consent of the paper.

For safety, in this trial, we do not accept the oral informed consent and the case that re-sign the informed consent after the operation.

### 4.3 Patient Screening Process

Researchers need to understand the situation of new hospitalized maternal, such as the presence of potential subjects. Researchers also need to read their medical case reports in detail, and then confirm the inclusion criteria and exclusion criteria. When all the criteria meet, we need to get informed consent from potential subjects, and informed consent needs to be obtained prior to surgery. After receiving the informed consent, randomization will be performed directly in the delivery room at the time of preparation (in order to provide enough consideration to maternal time) and subjects will be assigned to the respective groups based on randomization results. The screening process needs to be recorded in the patient enrollment form.

### 4.4 Randomization Process

Once subjects are confirmed through all the criteria and have received the informed

consent, they can be randomized to either the treatment group(Caesarean section with IOCS) or control group(Caesarean section without IOCS).The randomization will be proceed in operation if the patient needs blood transfusion.

Randomization (ratio:1:1) is used through a network-based randomization system, which follows SOP. We use central dynamic randomization system.

The randomization will be stratified by 5 conditions:

1. centers
2. type of cesarean section (Emergency/Elective)
3. whether there exist abnormality in placental
4. number of fetus (twins or more)
5. whether the ASA level is in I – II?

The randomization system will be tested and validated before the trial starts and will be supervised by the leader center's CRA and statistical expert throughout the trial. Once the subjects have been successfully grouped, they will be recorded in the enrollment form.

Each test center has their independent account and password for randomization system. The account number and password are authorized to the relevant staff by the major researchers in each center. After the staff has filled in the subject's ID and details into the randomization system, the system will display the grouping result.

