### 3.2 Midway-Withdraw of Subjects

After completing randomization, the subjects will be considered as midway-withdraw from the study if:

[figure not shown]
- does not meet the inclusion criteria;
- for safety issue, one of the transfusion methods must be applied;
- subjects is no longer able to agree to participate the trial;
- subjects withdraw their consent form during the trial or during data collection;
- subjects no longer need cesarean section.

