#### 4.5 Methods of Minimizing Risk and Bias

Using a third party to hide the grouping will help reduce the errors caused by selection. The randomization will be proceed in operation, and the staff should set blinding to the subjects.

Operational errors could result in change in blood transfusion rate. To minimize this risk, we need to make sure that all operating rooms and recovery wards in each center use an unified blood transfusion plan. Each medical team within each center should have same start-up criterion for setting up blood transfusion. Before participating in the trial, each center should provide a blood transfusion plan to the leader center for record. Some centers would use a prespecified value of Hb to determine whether blood transfusion is needed and this value should be unified among each center's medical team. If any of the following symptoms presents, such as unconscious, dyspnoea, exhaustion, which could clearly indicate level of red cell, blood transfusion is needed. Maternal mobility and neonatal care after cesarean section are different from the postoperation rehabilitation activity of most bedridden patients. According to the practical issues, since the clinicians may have different point of view, it is allowed to have little variation between each center. It represents the difference in reality cross the clinic, so it will not increase the bias.

Postpartum ward medical staff should use an unified blood transfusion plan as far as possible, according to the postoperative Hb levels and maternal symptoms. Do not deliberately observe the grouping of subjects.

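### The plan gives two times for randomisation (at preparation in 4.3, in the operation in 4.4 and 4.5); under the earlier one, need for transfusion may be judged with the arm known, and no rule says who is then analysed

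*Combined protocol and SAP*

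**What the plan says.** All references are to the combined protocol and SAP.

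- **4.3 (screening):** eligibility is confirmed from the case notes and consent is taken before surgery. Then: "After receiving the informed consent, randomization will be performed directly in the delivery room at the time of preparation".
- **4.4 (randomisation):** "The randomization will be proceed in operation if the patient needs blood transfusion". After staff enter the woman's details, "the system will display the grouping result".
- **4.5 (bias):** "The randomization will be proceed in operation, and the staff should set blinding to the subjects". Blinding is thus of the women, not of staff.
- **4.7 (treatment plan):** its wording ties allocation to the haemoglobin level and the transfusion guideline, which fits allocation in the operation. Between 70 and 100 g/L the decision is left to the transfusion plan and the staff.
- **3.1.1:** need for transfusion during the caesarean is an inclusion criterion, resting partly on the obstetrician's or anaesthetist's advice.
- **3.2:** withdrawal after randomisation applies, among other reasons, if a woman "does not meet the inclusion criteria" or if "subjects no longer need cesarean section".
- **Analysis sets:** Table 1 names an FAS and a per-protocol set. Section 8.3.4 (Trial Population) defines neither.

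Sections 4.2.1 and 4.2.2 say only that randomisation is on the day of operation, which fits either timing.

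**The concern.** A centre cannot allocate both at preparation and in the operation once transfusion is needed. The choice matters because one inclusion criterion becomes certain only during surgery. Under 4.4 it is settled before the arm is known. Under 4.3, if read as anticipated need, it is settled afterwards, by staff who have seen the arm and who have discretion over part of the haemoglobin range.

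Some randomised women may then prove not to need transfusion. If they are left out, the comparison is restricted by a decision made after allocation, and the arms can differ in severity without any treatment effect. If they are kept, women who received neither form of transfusion dilute the contrast. The plan does not say which happens. Section 8.3.3 bases superiority partly on the sign of the difference in medians, which selection of this kind can move.

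**Working it through.** **1. Do the texts conflict?** Yes. Section 4.3 places allocation in the delivery room straight after consent; 4.4 and 4.5 place it in the operation. The early timing is not a single stray sentence: a woman who no longer needs a caesarean can be a withdrawal *after* randomisation (3.2) only if allocation came before surgery.

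**2. Does another rule settle who is analysed?** No. Section 3.2 does not name untransfused women; its inclusion-criteria item can be read to cover them. Section 3.3 asks for reasons, adverse events and follow-up of withdrawn women, but does not say whether they are analysed.

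**3. The plan's own figures, for scale.** Section 8.1.1: (1.96 × 709 / 200)² = 48.28, or 49 rounded up; the plan states 50. Then 1.2 × 50 = 60 per arm, 120 in total. The 200 ml is the margin of a precision formula, not a stated treatment effect.

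**4. Illustration if untransfused women are dropped.** The documents give no transfusion rate, so the rates and correlations below are assumptions.

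- Intraoperative severity S and a loss score Z are bivariate normal with correlation ρ. A woman in arm a is transfused if S exceeds the cut-off that gives proportion p(a). There is no treatment effect.
- Loss = Q(F(Z)), where F is the distribution of Z in transfused controls and Q follows the pilot table in 8.1.1: zero to the 25th percentile, linear to 274 ml at the median, linear to 700 ml at the 75th, then 700 plus a lognormal excess.
- Mean of the excess: 444 / 0.25 − (0 + 137 + 487 + 700) = 452. An SD of 1,093 for the excess returns the pilot SD of 709.

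Shift, IOCS minus control:

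| Transfused, control v IOCS | Mean, ρ = 0.3 / 0.5 / 0.7 | Median, ρ = 0.3 to 0.7 |
|---|---|---|
| equal rates | 0 / 0 / 0 ml | 0 ml |
| 80% v 85% | −10 / −16 / −21 ml | −10 to −26 ml |
| 40% v 60% | −45 / −74 / −104 ml | −44 to −123 ml |

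Swapping the two rates, with the pilot still matched to the control arm, reverses the sign: the mean shift is +10 to +22 ml and +49 to +122 ml.

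**5. Against sampling error.** The standard error of the mean difference is 709 × √(1/n₁ + 1/n₂).

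- 80% v 85% of 60 leaves 48 and 51: standard error 142.6 ml. A shift of 21 ml is 0.15 standard errors.
- 40% v 60% leaves 24 and 36: standard error 186.8 ml. A shift of 104 ml is 0.56 standard errors.

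By normal approximation, the chance of falsely favouring IOCS rises from 2.5% to about 3.5% and 8% respectively. These use the largest shift in each row. A comparison of means stands in for the log-rank test named in 8.3.3.

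**6. Loss and dilution.** With share q transfused in both arms, dropping the rest leaves 60q per arm; the 1.2 allowance is used up once q falls below 50/60 = 83%. Keeping everyone turns a difference D among transfused women into qD: taking D = 200 ml, 160 ml at q = 0.8 and 100 ml at q = 0.5.

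**The case against.** The sections that deal with allocation mostly agree. Sections 4.4 and 4.5 both say in the operation, and 4.7 fits. The 4.3 sentence applies only once all criteria are met, and one of those is need for transfusion. Harm therefore requires a centre both to follow 4.3 and to read that criterion as anticipated need. The 4.1 flow chart, the SOP that 4.4 cites and the randomisation system manual listed in 9.2 are not visible and may settle the timing. Section 4.5 also narrows discretion: "Each medical team within each center should have same start-up criterion for setting up blood transfusion", and certain symptoms require transfusion. All of this stands, and it makes in-operation allocation the likelier intent. It does not remove the conflict in the text, the withdrawal item that fits only early allocation, or the discretion left by 4.7.

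A reader might go further and infer any of the following. The documents do not support them.

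- *That 3.2 excludes untransfused women from the analysis.* This is one reading; 3.2 speaks of withdrawal, not of analysis sets.
- *That 3.3 concedes this bias.* Its remark that "it is unavoidable that those midway-withdraw subjects will lead to biased outcome" concerns withdrawals in general.
- *That the bias favours IOCS.* The advice in 4.7 to use donor blood sparingly, and the obstetricians' preference for salvage in 1.4, could suggest a lower threshold in that arm. Neither shows it, and the opposite gap gives the opposite sign.
- *That a lower median alone would yield a superiority claim.* Section 8.3.3 also requires p ≤ 0.05.
- *That allocation in the operation means every randomised woman is analysed.* Consent withdrawal and the other reasons in 3.2 and 3.3 still apply.

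**Conclusion.** The concern holds in conditional form. The plan contains two incompatible allocation times, nothing visible ranks them, and the analysis population is undefined. If all centres allocate as 4.4 says, the selection problem largely disappears. If any centre allocates as 4.3 says and treats need for transfusion as anticipated, the result is open to selection bias in either direction, or to dilution, depending on a choice the plan leaves unmade.

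The size cannot be derived from the documents. On the assumed rates it runs from zero (equal rates), through 10 to 21 ml (80% v 85%), to 45 to 104 ml (40% v 60%) in the difference in means. Given the common transfusion criterion within each centre, a 20-point gap is a severe assumption. The point should be corrected because the ambiguity is avoidable and cheap to remove, not because a large bias has been shown. Confidence is medium, since the flow chart, SOP and system manual could not be read.

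**What to change.** 1. **4.3:** delete the randomisation sentence. Allocate in the operation, after the transfusion decision and its trigger (haemoglobin value or symptom) are entered in the randomisation system and before it shows the arm.
2. **3.2:** treat failure of the inclusion criteria, and no longer needing a caesarean, as screening failures before allocation.
3. **8.3.4:** define the FAS as all randomised women in their allocated arm and make it the primary set. Keep in it any women already allocated at preparation, and report by arm how many there were.
4. **Appendix 3:** state that salvage suction and reservoir are set up in the same way for all consented women before allocation, with processing and reinfusion only in the IOCS arm. The appendix prepares suction before the operation and collects blood before the transfusion trigger; without this rule, blood shed before allocation would be lost.

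**Cost:** wording changes, two mandatory fields in the existing web system, and collection consumables for control women and consented women who are never randomised. The last item is small if the recycling-machine volume in 4.9.1 is already measured in both arms, which the text does not settle. No extra patients or visits are needed.

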# Introduction

## 1.1 Background

Haemorrhage(excessive blood loss) is one of the major causes of maternal death. It is more likely to occur during caesarean section, especially for those maternal who have placenta accreta or placenta previa.

Blood is a scarce and expensive resource. Hospitals in China at all levels have varying degrees of tension with blood. Due to the scarcity of blood and maternal's risk of blood transfusions, it is common that mothers lose their blood transfusions in time, and result in postpartum anemia (low hemoglobin levels) in their mothers. A series of reports confirmed: anemia is a direct cause of maternal deaths. Life-threatening blood loss is an indication of emergency hysterectomy. A retrospective analysis involving 24 hospitals shows that at present, the total domestic cesarean section rate is 57.84% (2005 ~ 2006). Postoperative anemia will further prolong hospitalization, increase postoperative infection rates and delay the time of first mobilisation. Intraoperative cell salvage collects patients' own lost blood, wash and filter into the patient's own blood circulation. It may help to reduce the incidence of postoperative anemia for patients and avoid prolonged hospitalization. Although it has been confirmed that using cell salvage technology in some operations can reduce allogeneic blood transfusion, since clinical concerns about the amniotic fluid contamination of the blood transfused by the mother, intraoperative cell salvage during caesarean section has not yet been fully validated. At present, the National Institute of Health and Clinical Excellence has developed guidelines which recommend to use intraoperative cell salvage in the event of excessive haemorrhage in emergency cesarean section. In addition, intraoperative cell salvage is also recommended by the Royal College of Obstetricians and Gynecologists and the American Society of Anesthesiologists. At present, only a few clinical cases in China have been reported for washing autologous blood transfusion for maternal hemorrhage. No relevant randomized controlled studies were found in the literature. The risks of allogeneic blood transfusion include: death from transfusion errors, acute transfusion reactions, fatal lung injury and infections. Therefore, applying allogeneic blood transfusion to the healthy maternal need to be very cautious, and intraoperative cell salvage may possibly avoid these risks. Intraoperative cell salvage is a technique that can not only simultaneously reduce the need for allogeneic transfusions and prevent anemia, but also avoid bleeding-related serious complications. It has been shown to be well documented in non-cesarean sections, but current information is not able to demonstrate the safety and efficacy of autologous blood collection for bleeding during cesarean section, and have reported several cases of coagulation dysfunction associated with autologous blood collection. Therefore, it is necessary to carry out the monitoring of coagulation function and other checking of related

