### 2. Sample Size Estimation Based On Population Mean

$$n = \left(\frac{t_{\alpha/2} s}{\delta}\right)^2$$

If  $t_{0.05}=1.96$ ,  $S=709$ ,  $\delta=200$ , the estimated minimum sample size is 50.

3. Thus, according to ratio 1:1, the sample size of IOCS group is also 50.

4. Taking into account the unpredictable factors in the experiment that cause the loss of sample size, we recommend to use 1.2 times the minimum sample size as the sample minimum sample size. Therefore, according to ratio 1:1 between treatment group and control group, the total sample size would be 120 (where 60 for treatment group, and 60 for control group).

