## 8.3 Statistical Methods

### 8.3.1 General Principle

Using SAS 9.13 for statistical analysis. All statistical tests should be two-sided. If p-value is less or equal to 0.05, then it is considered to be statistically significant.

Variables data are described by mean±standard deviation, median, maximum and minimum. Use paired t-test to compare intra-group variations with respect to baseline and use ANOVA or Wilcoxon rank-sum test to compare variations between groups.

Attributes data are described as frequency (percentage). Between group comparison of percentages is tested by Fisher's exact test

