### 8.3.3 Hypothesis Test

Primary objective: The amount of blood lose post operation:

$$H_0: HR = \frac{\lambda_T}{\lambda_C} < 1, \quad H_1: HR = \frac{\lambda_T}{\lambda_C} \geq 1$$

$\alpha = 0.05$  (two-sided).

By Log-Rank test, if p-value is less or equal to 0.05, and the median amount of blood lose in treatment group is less than in control group, then the superiority of the treatment group relative to the control group holds.

Based on the Cox Proportional hazards model, hazard ratios and the 95% confidence interval (CI), if the lower bound of the CI is greater than 1, then the efficacy of the treatment group is better than that of the control group.

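### The five randomisation factors appear in none of the planned between-group analyses, so the comparison is conservative and loses power if the factors predict blood loss

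*Combined protocol and SAP*

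**What the plan says.** Section 4.4 allocates women 1:1 and states "The randomization will be stratified by 5 conditions". The factors are centre (six sites), emergency or elective section, placental abnormality, number of fetuses and ASA class. On the mechanism it says "We use central dynamic randomization system", without naming the algorithm.

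For continuous data, section 8.3.1 says to "use ANOVA or Wilcoxon rank-sum test to compare variations between groups". It assigns Fisher's exact test to percentages. For the primary objective, section 8.3.3 uses a log-rank test together with a Cox hazard ratio and its confidence interval. None of these mentions a covariate, a stratum or a centre effect. Section 8.3.4.2 lists age, height, weight and history, but only for comparing the arms at baseline. The synopsis row on statistical method gives analysis sets and software only.

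**The concern.** Dynamic balancing removes most of the chance difference between arms on the chosen factors. If those factors predict the outcome, the treatment estimate varies less than it would under simple randomisation. An unadjusted t-test, ANOVA, rank test or log-rank test does not register this. It leaves the factors' variance in its error term, so its standard error is too large, its actual level is below 5%, and it has less power than a test that includes the factors.

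The plan itself gives grounds for thinking some factors matter. Section 1.1 says haemorrhage at caesarean is more likely "especially for those maternal who have placenta accreta or placenta previa". On transfusion practice, section 4.5 says "it is allowed to have little variation between each center", and the blood-loss formula in 8.1.1 adds transfused red-cell volume, so a centre difference can enter the outcome directly. A trial of 120 women with an SD of 709 ml has little precision to spare. Silence in 8.3 also leaves the choice between adjusted and unadjusted results open until the data are seen.

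**Working it through.** **Inputs from the plan (8.1.1 and 8.3):** SD 709 ml, δ = 200 ml, 60 women per arm, two-sided α = 0.05. The plan gives no power and no R². R² here means the share of blood-loss variance explained by the five factors; it is an assumption.

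**The plan's own figure.** n = (1.96 × 709 / 200)² = 48.3, so 49. The plan says "the estimated minimum sample size is 50", which is close. Then 50 × 1.2 × 2 = 120.

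**Formula check, taking the factors as perfectly balanced.**
- Reported unadjusted SE = 709 × √(2/60) = 129.4 ml.
- True SE = 129.4 × √(1 − R²).
- Critical difference = 1.96 × 129.4 = 253.7 ml.

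At R² = 0.3 the true SE is 108.3 ml, which gives:
- Unadjusted type I error = 2[1 − Φ(253.7/108.3)] = 2[1 − Φ(2.34)] = 1.9%.
- Unadjusted power for 200 ml = 1 − Φ((253.7 − 200)/108.3) = 1 − Φ(0.50) = 31.0%.
- Adjusted power = 1 − Φ(1.96 − 200/108.3) = 1 − Φ(0.11) = 45.5%.

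The n per arm for 80% power is 2(1.96 + 0.84)² × 709²(1 − R²)/200², rounded up.

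| R² | Type I error, unadjusted | Power, unadjusted | Power, adjusted | n per arm for 80%, adjusted |
|---|---|---|---|---|
| 0 | 5.0% | 33.9% | 33.9% | 198 |
| 0.1 | 3.9% | 33.1% | 37.0% | 178 |
| 0.2 | 2.8% | 32.1% | 40.8% | 158 |
| 0.3 | 1.9% | 31.0% | 45.5% | 139 |

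**Simulation with imperfect balance.** Assumptions: Pocock–Simon minimisation with an 85% biased coin, n = 120, centre shares 30/20/15/15/10/10%, binary factor prevalences 40/50/15/60%, equal contributions to R², normal outcome, 5,000 runs per setting (Monte Carlo SE about 0.3 points for type I error and 0.7 for power). The unadjusted t-test is compared with a linear model containing the factors as main effects.

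| R² | Type I error, unadjusted | Power, unadjusted | Power, adjusted |
|---|---|---|---|
| 0 | – | 34.2% | 33.4% |
| 0.1 | 4.5% | 32.5% | 36.0% |
| 0.2 | 3.4% | 32.4% | 40.0% |
| 0.3 | 2.8% | 31.7% | 44.0% |

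Adjusted type I error was 5.2% to 5.4%. The 95% CI half-width falls from 256 ml to about 246, 231 and 216 ml at R² = 0.1, 0.2 and 0.3.

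**Sensitivity of these results.**
- *Simulation settings:* across all sets run, unadjusted t-test type I error at R² = 0.3 ranged from 1.2% to 2.8%, and adjusted type I error from 3.8% to 5.8%. The direction never changed.
- *Rank regression:* power rises from 31.5% to 34.4% (R² = 0.1) and from 29.6% to 40.9% (R² = 0.3), with adjusted type I error about 5.5%.
- *Unadjusted log-rank, the test named in 8.3.3:* type I error 5.0%, 4.2% and 3.0%, and power for 200 ml 30%, 28% and 27%, at R² = 0, 0.1 and 0.3.
- *Permuted blocks of four in the strata instead of minimisation:* unadjusted type I error is 4.7% (R² = 0.1) and 3.2% (R² = 0.3). Power still rises, from 34.1% to 36.7% and from 31.8% to 44.1%.
- *Skewed outcome shaped on the pilot quantiles, R² set on the latent scale:* the gain is about 2.5 to 3 points at R² = 0.1 and 8 to 11 points at R² = 0.3.
- *Factors added to the Cox model:* the adjusted Wald test ran at 7.2% to 7.9% for a normal outcome and 5.3% to 6.5% for a skewed outcome with 25% zeros. The log-hazard-ratio interval was no shorter (half-width 0.38 against 0.36).

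**The case against.** The omission itself is not in dispute; the argument is about its size.

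- **The factors may be weak predictors.** The primary objective is postoperative loss over five days (2.1.1), whereas section 1.1 concerns bleeding at caesarean. All randomised women already have raised risk and need transfusion. Section 4.5 asks for a unified plan, and 4.7 ties transfused volume to a common formula within ±15%. The documents offer nothing on ASA class, number of fetuses or urgency as predictors of postoperative loss. This stands as a reason to treat R² = 0.3 as an upper scenario.
- **The pilot is dominated by its tail.** The largest value alone contributes (4347 − 444)²/(47 × 709²) = 64% of the pilot sum of squares, which leaves baseline factors little regular variance to explain. This stands: with that shape the gains shrink, though the direction holds.
- **The 200 ml is a precision half-width in a one-sample formula.** It is not a stated treatment difference, and power is nowhere claimed. The 34% is therefore a benchmark.
- **The loss is relative to the adjusted analysis.** For a 363 ml difference, unadjusted power rises from 80.0% at R² = 0 to 84.3% at R² = 0.3. Adjusted power at R² = 0.3 is still higher, at 91.8%.
- **The shortfall in level depends on an algorithm the plan does not name.** With blocks of four and R² = 0.1 it is negligible.
- **The plan is silent rather than excluding adjustment, and 8.3.3 needs a settled primary model first.** ANOVA could carry the factors, but nothing says it will. The order of repair is a fair point and is reflected in the fix.

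**Conclusion.** The concern holds. Allocation is balanced on five factors and no between-group analysis in 8.3 uses them. If they are prognostic, the unadjusted comparison is conservative and less powerful than an adjusted one. For a normal outcome and a 200 ml difference, the simulated gain from adjustment is about 3.5 points of power at R² = 0.1 and 12 points at R² = 0.3, less with pilot-like skew. If the factors explain nothing, adjustment costs about a point.

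R², factor prevalences, centre shares and the biased-coin probability are all assumed, so the direction is firmer than the size. This is a matter of efficiency and pre-specification, not of false positives. It does not cure the trial's low power: even at R² = 0.3, 80% power for 200 ml needs about 139 women per arm against 60 planned.

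**What to change.** 1. Settle the primary model first. Sections 8.3.1 and 8.3.3 name different methods for the same blood volume.
2. State in 8.3 that the primary comparison is a linear model on blood loss in ml containing treatment and the five randomisation factors as main effects. A model on ranks, with a separate estimate in ml, is an alternative.
3. Set a rule in advance for pooling very small centres. Do not cross the factors: 6 × 2⁴ = 96 cells is too many for 120 women.
4. Report the unadjusted result as supportive.
5. Do not simply add the nine factor terms to the Cox model in 8.3.3, given the inflated level seen in simulation.
6. Name the dynamic algorithm in 4.4, since the shortfall in level depends on it.
7. Preoperative haematocrit may be added for precision. It is not a balancing factor, so the argument about type I error does not apply to it.

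The cost is a short change to 8.3, about 10 degrees of freedom out of 120 women, and up to 1 to 2 points of power if the factors turn out not to be prognostic. All five factors are already held in the randomisation system.
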